## 17. FERTILITY INTENTIONS ASSESSMENT

CDC/DHHS guidelines on use of PrEP in women include guidance on counseling serodiscordant couples who want to conceive a child (73, 74). Periconception use, or “PrEPception” (75), is a potential area in which PrEP may be beneficial in reducing risk of HIV acquisition. As a result, women will not be excluded based on fertility intentions. Fertility intentions will be assessed as part of the initial intake at baseline, and pregnancy testing will be performed at follow-up visits for monitoring as outline in the schedule of events. As detailed in the MOPS, the study will use a designated Informed Consent for women who become pregnant on-protocol, and a separate complementary schedule of follow-up for pregnant women, who will be followed in clinical collaboration with high-risk obstetric (Maternal Fetal Medicine Service) providers.

## 18. STUDY ASSESSMENTS

The 10 domains to be covered include:

- a. Adherence
- b. Substance Use
- c. Sexual Behavior/Risk
- d. Psychosocial Constructs
- e. PrEP Efficacy
- f. Willingness to Take PrEP
- g. Violence and Trauma
- h. Healthcare and Referrals
- i. HIV Knowledge and Perception
- j. Family Planning

At the screening visit, CASI-based assessments will be administered which will include the domains of Sexual Behavior/Risk, PrEP efficacy, Willingness to take PrEP, Violence and Trauma and HIV knowledge and Perception and Family Planning.

At the baseline visit, additional CASI-based assessments will be administered which include Adherence, Substance Use, Psychosocial Constructs, Violence and Trauma and Healthcare and Referrals.

During follow-up visits (4, 12, 24, and 36 weeks) CASI-based assessments will continue which will include Adherence, Substance Use, Sexual Behavior/Risk, Psychosocial Constructs, Violence and Trauma and Healthcare and Referrals, and Family Planning.

At the End of Study (week 48) visit, CASI-based assessments will include, in addition to above, PrEP efficacy and HIV knowledge and Perception.

Study visits will also include discussions with study staff about substance use, depression and domestic violence. Concern about substance abuse will trigger referral for substance abuse counseling. A screen for depression and/or psychological distress or any request for mental health services will trigger referral for appropriate mental health services. Any report or suspicion of domestic/partner violence will trigger referral for appropriate partner services.

In terms of risk reduction counseling, all participants will be provided a sexual health counseling session at every study visit starting at baseline (see below). All participants will be counseled that condoms should be used for all forms of penetrative non-oral sexual contact.

*Full contents of the CASI and assessments will be specified in MOPS.*

## **19. RISK REDUCTION COUNSELING INTERVENTION**

As noted above, the iNSC addresses both behavioral and biomedical strategies to promote protection of sexual health. iNSC will be provided at each study, preferably early in the study visit and in conjunction with delivery of an HIV-uninfected rapid test result. The structure of the intervention is provided above in section 16.5.3 and detailed in the MOPS.

## 20. SCHEDULE OF CLINICAL AND LABORATORY EVALUATIONS

Table 1. Schedule of Evaluations							
	Screen	Study Weeks of Follow-up				Interim	
	Within 28 days	Baseline	Wk 4	Week 12 and every 12 weeks	End of Study or premature D/C	Suspected HIV or STI infection	Interim for Missed Visit
Visit Window		± 14 days					
Informed Consent	X						
Demographics	X						
Locator Form	X						
Medical/Medication History	X						
Concomitant medications	X	X	X	X	X	X	X
Limited physical exam	X	X	X	X	X	X	X
Clinical assessment	X	X	X	X	X	X	X
Fertility intent assessment	X	X	X	X	X	X	X
Contraceptive counseling	X	X	X	X	X	X	X
Domestic/partner violence assessment	X	X	X	X	X	X	X
Systems review and iTAB setup		X					
PrEP dispensation		X	X	X			
Adherence/ risk reduction/ Sexual health counseling		X	X	X	X	X	X
Self-reported tablet assessments 	X	X	X	X	X	X	X
PrEP adherence assessment			X	X	X	X	X
Laboratory							
HIV EIA/VL or Ag/Ab 	X						
Rapid HIV Test		X	X	X	X	X	X
HBsAg and HBsAb	X						
Urine beta HCG	X	X	X	X	X	X	X
Cr and GFR	X		X	X	X	X	X
LFT and CBC		X					
Serum RPR		X		[X]	[X]	X	[X]
3-site STI Screening		X		[X]	[X]	X	[X]
HSV-2 Screening		X			X 		
DBS for RBC TFV-DP			X	X	X	X	X
Banked plasma specimen 			X	X	X	X	X
HIV RNA, CD4, genotype						X	
Whole blood						X	

Table 1. Schedule of Evaluations							
	Screen	Study Weeks of Follow-up				Interim	
	Within 28 days	Baseline	Wk 4	Week 12 and every 12 weeks	End of Study or premature D/C	Suspected HIV or STI infection	Interim for Missed Visit

 Domains include: Adherence, Substance Use, Sexual Behavior/Risk, Psychosocial Constructs, PrEP Efficacy, Willingness to Take PrEP, Violence and Trauma, Healthcare and Referrals, HIV Knowledge and Perception, and other instruments.
 
 Positive or indeterminate rapid HIV ELISA testing will be confirmed with a viral load. If baseline occurs > 28 days after screening, HIV EIA/VL must be repeated.
 
 Plasma will be drawn and stored at indicated time points. If seroconversion to HIV occurs, these samples will be run fl or HIV-1 RNA (viral load) and genotyping.
 
 In case of seroconversion, sample to be shipped to UCSF and used for determining viral reservoir during hyperacute HIV infection.
 
 Repeat HSV-2 screening at Week 48 or End of Study only if negative at Baseline.
 
[X] Weeks 24 and 48 months only
							

## **21. CLINICAL ASSESSMENTS**

### **21.1. Complete Physical Exam**

A complete physical exam will be done at baseline and documented in the source documents only. A complete physical examination is to include an examination of the skin, head (including eyes and nose), mouth, and neck; auscultation of the chest; cardiac exam; abdominal exam, genital exam (as needed), skin exam, examination of the lower extremities for edema, and a brief neurological assessment. The complete physical exam will also include signs and symptoms, height in centimeters/inches, weight in kilograms/pounds, diagnoses, and vital signs (temperature (°C), pulse, respiration rate, and blood pressure).

### **21.2. Targeted Physical Exam**

Targeted physical exam will be done at all visits subsequent to the baseline visit and documented in the source documents only. A targeted physical examination is to include height in centimeters, vital signs (temperature, pulse, respiration rate, and blood pressure) and is to be driven by any previously identified or new signs or symptoms including diagnoses that the participant has experienced since the last visit. Staff should inquire about symptoms, as indicated.

### **21.3. Review of Systems**

A complete review of systems will be done at baseline and reviewed at all subsequent visits. This should be documented in the source documents only. Review of systems is to be driven by any previously identified or new signs or symptoms including diagnoses that the participant has experienced since the last visit.

### **21.4. Concomitant Medications**

Concomitant medications will be assessed at initial intake, reviewed at every study visit, and recorded on the appropriate CRF. Include actual or estimated start and stop dates. All concomitant medications (prescription and non-prescription) including alternative/complementary medications (e.g., herbs, vitamins, etc.) taken within 30 days prior to enrollment and anytime thereafter during study participation will be collected in the study participant's chart and recorded on the appropriate CRF. Concomitant medication lists will be reviewed by program pharmacy staff for potential drug interactions as appropriate.

## **22. HIV LABORATORY TESTING**

Rapid or conventional ELISA testing will be used. All positive rapid EIA results will be confirmed with both a conventional blood EIA test and a viral load (negative rapid tests are not further confirmed, except as per individual study site policy, and positive conventional blood EIA tests are only confirmed by viral load testing). As indicated in the protocol, 4th generation test (Ag/Ab), or NAAT testing in addition to EIA, will be used at screening and entry to exclude occult primary/acute HIV infection.

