#### 4. STUDY SCHEMA

- Design: AEGIS is an open-label single-arm longitudinal clinical trial to estimate medication adherence and retention in a PrEP HIV prevention program that implements a combination intervention strategy that uses text-messages (iTAB) and a staged adherence counseling support strategy titrated from real-time drug levels in women at-risk for HIV acquisition.
- Duration: Each participant will be on PrEP with medication adherence support for 48 weeks after enrollment with a post study follow-up at 60 weeks. The primary endpoint will be measured at 48 weeks.
- Sample Size: A total of 135 participants will be enrolled (50 at CCTG sites and 85 at the LAC-PATH site).
- Study Population: Eligible participants will include HIV-uninfected cis-gender women at least 18 years of age and who are at risk for HIV acquisition.
- Intervention: All participants will be given PrEP with tenofovir disoproxil fumarate (TDF) + emtricitabine (FTC) fixed dose combination prescribed to be taken once daily. All participants will receive the combined intervention of iTAB text messaging adherence reminders and intensive Next Step Counseling (iNSC). The iTAB system consists of daily, personalized, automated 2-way text messages to maintain adherence and retention, and iNSC is a brief, strengths-based discussion initiated at each clinic visit, typically with delivery of negative HIV-test results, focused on promotion of sexual health protection through behavioral and biomedical (adherence) strategies. Participants that have a low intracellular tenofovir diphosphate (TFV-DP) concentration will receive escalated, targeted adherence support (see study schema). All participants will receive access to PrEP in accordance with standardized comprehensive methods of prescribing and clinical assessments that include safety monitoring as well as regular HIV and sexually transmitted infection (STI) screening.
- Regimen: TDF 300 mg + FTC 200 mg fixed dose combination will be given orally once daily starting at the baseline visit (month 0) and continued throughout the study.

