**12. ENROLLMENT OF PARTICIPANTS**

Potential participants will be screened for a combination prevention intervention. After the participant reviews and signs the informed consent document, receives HIV testing (including 4th generation test or ELISA and nucleic acid amplification (NAAT) testing) to confirm HIV-uninfected status, and is evaluated using the inclusion and exclusion criteria, she will be considered enrolled in the protocol.

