### 15.1. Screening

At a screening visit, Informed Consent will be reviewed. An intake of inclusion and exclusion criteria will be performed by program personnel. HIV-testing (4th generation test, or EIA and HIV RNA) and screening laboratories as noted in the Schedule of Evaluations (SOE) will be performed. If all inclusion and no exclusion criteria are met, a baseline visit will be scheduled within 28 days. A detailed locator form will be completed including primary contact telephone, paper-mail, email, social-network, and emergency contact information. This information will be verified at each subsequent visit for changes and/or updates. At screening, individuals will also be asked to complete a brief computer assisted self-interview (CASI)-based assessment evaluating HIV risk; PrEP awareness, barriers and facilitators; and willingness to take PrEP.

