The main difference between iNSC and targeted iNSC focused on exploring whether or not PrEP is something the participant wants to continue with (given low drug level and relatedly low afforded PrEP benefit), and if so a strengths-based exploration (when dosing did occur, what facilitated it) precedes exploration of specific barriers to dosing (what specifically prevented consistent dosing), needs are identified, strategies discussed and an adherence plan created. Because participants all engage in iTAB, plans will also emphasize use of iTAB to ask for help. Participants no longer interested in PrEP will be engaged in discussion around that decision and their plan for how to stay HIV negative using other strategies discussed.

PrEP-STEPS is a four-session weekly intervention with two subsequent monthly booster sessions modeled after an evidence-based ART adherence intervention (LifeSteps) which is a Cognitive Behavioral Therapy (CBT)-based counseling approach to facilitate PrEP adherence. This program will be deployed at in-person sessions and is the highest intensity level intervention.

The 3 interventions will be used as three “stages” or levels of intensity of adherence support. One intervention is deployed for a given participant, titrated based on the history and chronology of real-time measured DBS TFV-DP levels.

All participants will receive iNSC at the baseline/entry visit and at all subsequent visits [see the MOPS for structure of the standard iNSC intervention]. Suboptimal adherence (TFV-DP levels of <1050 fmol/punch (representing fewer than mean 6-7 daily doses per week)) will trigger “targeted iNSC” which will be implemented when drug levels are obtained by the site- typically about 10 days after the clinic visit (72). Participants in this sub-optimal range are contact by the counselor, informed of their results and asked to come in for a specific conversation (targeted iNSC). This first level of more intensive support may be deployed by telephone or in person. There will not be additional compensation for participating in these sessions. Details of the targeted iNSC intervention are provided in the MOPS. If this is a repeat sub-optimal level the counselor schedules the participant for the first of 4 (+2 booster) PrEP-Steps sessions.

Details of the PrEP-STEPS Program with Content Optimized for Women program are provided in the MOPS.

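### Section 22 calls for an acute-infection HIV test at baseline that Table 1 does not schedule, and the first banked plasma, at week 4, is too late to date an early infection relative to PrEP start

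*Combined protocol and SAP*

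**What the plan says.** All references are to the combined protocol and SAP.

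- **Section 22** says the sensitive test (fourth-generation Ag/Ab, or NAAT in addition to EIA) "will be used at screening and entry to exclude occult primary/acute HIV infection". It also says that "negative rapid tests are not further confirmed, except as per individual study site policy".
- **Section 16.5.3** fixes what entry means: "All participants will receive iNSC at the baseline/entry visit and at all subsequent visits".
- **Table 1 (Section 20)** has a row "HIV EIA/VL or Ag/Ab" marked in the Screen column only. The rapid HIV test is marked from Baseline onward and is the only HIV test scheduled at baseline.
- **Table 1, footnote 2** requires a repeat only if baseline falls more than "28 days after screening, HIV EIA/VL must be repeated".
- **Section 15.1** places the sensitive test at screening and adds: "If all inclusion and no exclusion criteria are met, a baseline visit will be scheduled within 28 days".
- **Section 12** lists the test among the steps before enrolment, "nucleic acid amplification (NAAT) testing) to confirm HIV-uninfected status", without naming a visit.
- **Section 4** starts daily dosing at the baseline visit.
- **Section 24 and Table 1** store plasma from week 4 onward, with none at screening or baseline.
- **Table 2, footnote 2 (Section 27.4)** runs viral load backward through stored plasma after a seroconversion until it is undetectable.
- **Sections 5.2.8 and 5.2.9** make HIV incidence, and resistance among seroconverters, secondary objectives.

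**The concern.** There are two separate points.

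The first is a conflict within the current text. Section 22 gives the purpose of the sensitive test, which is to keep women with unrecognised acute infection off PrEP, and places it at both visits. A site that works from Table 1 runs it once and relies on a rapid test on the day of dispensing. Because site policy decides whether a negative rapid test is followed up, practice could differ across the five sites.

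The second concerns specimens and is not an inconsistency, since Table 1 and Section 24 agree with each other. If a woman is rapid-negative at baseline and viremic at week 4, the backward look-back has no earlier plasma to test. Whether she was infected before or after her first dose cannot then be verified.

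At stake are the attribution of an infection to the on-PrEP period and the reading of any resistance found in it. There is also a safety side. Section 6 reports M184V in two participants of an earlier trial in men who have sex with men; both were in the window period at entry and were given active TDF/FTC. The protocol is already stricter elsewhere: Section 28.1 requires a negative rapid EIA and a viral load before restarting after more than 14 days off drug, whereas a first dose may follow the last sensitive test by 28 days with a rapid test alone.

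**Working it through.** The plan states no figure on this point, so there is none to reproduce. The check compares the texts, then sizes the gap.

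**1. The texts side by side**

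| Source | Sensitive test at screening | Sensitive test at baseline |
|---|---|---|
| Section 22 (with 16.5.3) | yes | yes |
| Section 15.1 | yes | not mentioned |
| Table 1 | yes | no (rapid test only) |
| Table 1, footnote 2 | yes | only if the gap exceeds 28 days |

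Section 22 is the outlier.

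**2. Length of the interval without an RNA-informative specimen**

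- Screening to first dose: up to 28 days. First dose to first banked plasma: 28 days.
- Total: 28 + 28 = 56 days, or 70 if the 14-day visit window applies to week 4.
- Share lying before PrEP start: 28/56 = 50% at the maximum gap; with a 7-day gap (assumed), 7/35 = 20%.
- With plasma stored at baseline, the interval falls to 28 days, all after the first dose apart from the period in which RNA is not yet detectable.

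**3. Expected number of cases**

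Inputs: 135 women (Section 4). The protocol gives no incidence, so 0.5 to 3 per 100 person-years is assumed. Expected cases = 135 × days/365.25 × rate.

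| Interval | Person-years | Expected cases | Chance of at least one, 1 − exp(−m) |
|---|---|---|---|
| Screening to baseline, average 14 days (assumed) | 5.17 | 0.03 to 0.16 | 2.6% to 14.4% |
| Screening to baseline, all 28 days | 10.35 | 0.05 to 0.31 | 5.0% to 26.7% |
| Screening to week 4, 42 days | 15.52 | 0.08 to 0.47 | 7.5% to 37.2% |
| Screening to week 4, 56 days | 20.70 | 0.10 to 0.62 | 9.8% to 46.3% |

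The first two rows concern infections present at the first dose. The last two concern infections whose timing could not be verified. All are upper bounds for infections acquired after screening: nothing is deducted for cases caught by the baseline rapid test or the symptom exclusion, and no PrEP effect is taken off.

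**4. Effect of one case on the incidence estimate**

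- Full follow-up of 135 women for 336 days (Section 16.3): 135 × 336/365.25 = 124.2 person-years.
- No events: 0 per 100 person-years, exact Poisson 95% CI 0 to 2.97.
- One event: 100 × 1/124.2 = 0.81, exact 95% CI 0.02 to 4.49.
- With 100 women followed (92.0 person-years): 0 (0 to 4.01) against 1.09 (0.03 to 6.06).

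The intervals overlap widely, but a single case could be the whole incidence numerator and the whole resistance sample.

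**The case against.** The strongest case on the other side has four parts.

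- **The texts can be reconciled.** A reader might infer that a site cannot obey both Section 22 and Table 1. The documents do not support that. Table 1 does not forbid an extra test, so a site that runs the sensitive test at both visits complies with everything. What stands is that a site following Table 1 alone falls short of Section 22.
- **The woman can still be classified.** A reader might infer that a case viremic at week 4 is lost to the incidence and resistance objectives. She is not. She was negative at screening and at baseline, so a convention could class her as incident, and she stays in the summary of resistance among seroconverters. What stands is that attributing her infection to the on-PrEP period would be a convention that no specimen can check. Section 30 gives no rule; the later formal SAP may add one, but it cannot recover plasma that was never stored. Section 7 mentions stored whole blood for pharmacogenomics, but gives no collection time and no plan for HIV RNA.
- **Safeguards exist.** These are the screening test, the baseline rapid test, the exclusion for symptoms of primary infection (Section 14), a 4-week first supply (Section 16.4), a week-4 rapid test, and immediate EIA with viral load or NAT when acute infection is suspected (Section 27.3). Site policy and the MOPS may add more. As written, they do not reliably cover an asymptomatic, rapid-negative woman.
- **The count is tiny and rests on an assumed incidence.** This is accepted. The two resistance cases in Section 6 cannot be scaled to this trial, because the protocol does not describe that trial's entry testing and the population differs.

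**Conclusion.** The wording conflict is real: under Table 1 a site omits a pre-dose acute-infection test that Section 22 states. The lack of baseline plasma is a design weakness, not an error or a contradiction. It affects only women viremic at week 4; a later seroconverter with undetectable week-4 RNA can be placed after PrEP start.

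The size is small. Well under one case is expected on an assumed incidence of 0.5 to 3 per 100 person-years. The highest figure, 0.62, needs the top of that range, a 28-day gap for every woman and no PrEP effect. One case would move incidence from 0 to about 0.8 per 100 person-years, assuming full follow-up of all 135 women.

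The TFV-DP primary endpoint is unaffected, and nothing here should be read as casting doubt on it. The point is a minor improvement, worth making because it is cheap and the missing specimen cannot be obtained afterwards.

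**What to change.** 1. **Bank plasma at baseline.** Add Baseline to the banked-plasma row of Table 1 and to Section 24, using the blood already drawn for LFT, CBC and RPR. Run RNA and genotype on it only in seroconverters. Report a woman with RNA-positive baseline plasma as a prevalent infection, outside the incidence numerator and shown separately in the resistance summary. Report a woman who is RNA-negative at baseline and viremic at week 4 as incident, noting that infection too early for RNA detection cannot be excluded.
2. **Align Section 22 and Table 1.** Either add the Ag/Ab or EIA/VL test at baseline or, if the 28-day rule is what is intended, delete the words on entry from Section 22. If the test is added, name who promptly recalls a woman whose positive result arrives after dispensing; Sections 27.3 and 28.2 already cover resistance testing, referral and stopping drug. Step 1 is worthwhile under either choice.

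Step 1 costs one stored aliquot per woman (135), plus assays in seroconverters only. Step 2 costs one assay per woman (135) and a recall procedure, or only a wording change. Infections too early for RNA detection at baseline stay unresolved either way.

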## **23. ADDITIONAL LABORATORY TESTING**

### **23.1. STI Screening**

All participants will be screened at baseline for rectal (rectal swab), cervical (self-collected vaginal or urine) or pharyngeal (throat swab) gonorrhea and chlamydia using a verified NAAT test and for *T. pallidum* (syphilis) by serum treponemal/RPR testing. Asymptomatic STI screening will be conducted at 6-month intervals while on-study. Serologic testing for HSV-2 will be completed at Baseline, and again at Week 48 or End of Study if previously negative at Baseline. Positive results will trigger referral to appropriate private or SD/LA County STD program sites for treatment. Intervening signs or symptoms consistent with STIs should trigger referral to appropriate private or SD/LA county STD program services.

